7.2 Administrative Procedures

7.2.1 Informed Consent

The Investigator must obtain documented consent from each potential subject prior to participating in a clinical trial.

Consent must be documented by the subject's dated signature or by the subject's legally acceptable representative's dated signature on a consent form along with the dated signature of the person conducting the consent discussion.

A copy of the signed and dated consent form should be given to the subject before participation in the trial.

The initial informed consent form, any subsequent revised written informed consent form and any written information provided to the subject must receive the IRB/ERC's approval/favorable opinion in advance of use. The subject or his/her legally acceptable representative should be informed in a timely manner if new information becomes available that may be relevant to the subject's willingness to continue participation in the trial. The communication of this information will be provided and documented via a revised consent form or addendum to the original consent form that captures the subject's dated signature or by the subject's legally acceptable representative's dated signature.

Specifics about a trial and the trial population will be added to the consent form template at the protocol level.

The informed consent will adhere to IRB/ERC requirements, applicable laws and regulations and Sponsor requirements.

7.2.2 Inclusion/Exclusion Criteria

All inclusion and exclusion criteria will be reviewed by the investigator or qualified designee to ensure that the subject qualifies for the trial.

7.2.3 Medical History

A medical history will be obtained by the investigator or qualified designee. Medical history will include all active conditions, and any condition diagnosed within the prior 10 years that are considered to be clinically significant by the Investigator. Details regarding the disease for which the subject has enrolled in this study will be recorded separately and not listed as medical history.

The investigator or qualified designee will obtain prior and current details regarding disease status.

In the case of patients who have progressed to a metastatic stage after having been treated for early NSCLS stage, the investigator or qualified designee will review all prior cancer treatments including systemic treatments, radiation and surgeries.

7.2.4 Prior Medications

7.2.5 Concomitant Medications

The investigator or qualified designee will record medication, if any, taken by the subject during the trial. All medications related to reportable SAEs and ECIs should be recorded as defined in Section 7.2.

7.4 Assignment of Screening Number

All screened subjects will be given a unique *screening number* that will be used to identify the subject throughout the screening phase. Each subject will be assigned only one screening number. Screening numbers must not be re-used for different subjects. Any subject who is screened multiple times will retain the original screening number assigned at the initial screening visit.

After the PDL1 analysis, if positive result in the archival or newly obtained sample or previous PDL1 positive result, the subject will be included in the data base (Case report form, CRF) of the study that will assign the final *inclusion number* of the subject. Also, the screening number will be recorded in the CRF.

7.5 Clinical Procedures/Assessments

7.5.1 Adverse Event (AE) Monitoring

The investigator or qualified designee will assess each subject to evaluate for potential new or worsening AEs as specified in the Trial Flow Chart and more frequently if clinically indicated. Adverse experiences will be graded and recorded throughout the study and during the follow-up period according to NCI CTCAE Version 4.0. Toxicities will be characterized in terms regarding seriousness, causality, toxicity grading, and action taken with regard to trial treatment.

The investigator or qualified designee will perform a complete physical exam during the screening period. Clinically significant abnormal findings should be recorded as medical history. A full physical exam should be performed during screening.

7.5.4 Vital Signs

The investigator or qualified designee will take vital signs at screening, prior to the administration of each dose of trial treatment and at treatment discontinuation as specified in the Trial Flow Chart (section 6.0). Vital signs should include temperature, pulse, respiratory rate, weight and blood pressure. Height, weight and body surface will be measured at screening only.

[figure not shown]
7.5.5 Eastern Cooperative Oncology Group (ECOG) Performance Scale

The investigator or qualified designee will assess ECOG status at screening, prior to the administration of each dose of trial treatment and discontinuation of trial treatment as specified in the Trial Flow Chart(section 6.0).

7.5.6 Tumor Imaging and Assessment of Disease
·
Imaging assessment will be performed more frequently if clinically indicated.
7.5.7 Tumor Tissue Collection and Correlative Studies Blood Sampling

7.5.9 Blood Collection for Serum Pembrolizumab

Sample collection, storage and shipment instructions for serum samples will be provided in the Blood Samples Manual.

7.6 Other Procedures

7.6.1 Withdrawal/Discontinuation

When a subject discontinues/withdraws prior to trial completion, all applicable activities scheduled for the final trial visit should be performed at the time of discontinuation.

Any adverse events which are present at the time of discontinuation/withdrawal should be followed in accordance with the safety requirements, outlined in section 7.7 Assessing and Recording Adverse Events.

Subjects who a) attain a CR or b) complete 24 months of treatment with pembrolizumab may discontinue treatment with the option of restarting treatment if they meet the criteria specified. After discontinuing treatment following assessment of CR, these subjects should return to the site for a Safety Follow-up Visit and then proceed to the Follow-Up Period of the study.

7.6.2 Visit Requirements

Visit requirements are outlined in Trial Flow Chart (section 6.0). Specific procedure-related details are provided above in Trial Procedures.

7.6.3 Screening

7.6.4 Screening Period

Screening period will be 28 days from ICF signature.

7.6.5 Treatment Period

Extension of treatment with Pembrolizumab will be up to 24 months.

7.6.6 Post-Treatment Visits

Follow up visits are outlined in Trial Flow Chart (section 6.0)

7.6.7 Safety Follow-Up Visit

7.6.8 Follow-up Visits	
7.6.9 Survival Follow-up	
7.6.10 Subsequent Anti-Cancer Therapy Status	

7.7 Assessing and Recording Adverse Events

An adverse event is defined as any untoward medical occurrence in a patient or clinical investigation subject administered a pharmaceutical product and which does not necessarily have to have a causal relationship with this treatment. An adverse event can therefore be any unfavorable and unintended sign (including an abnormal laboratory finding, for example), symptom, or disease temporally associated with the use of a medicinal product or protocol-specified procedure, whether or not considered related to the medicinal product or protocol-specified procedure. Any worsening (i.e., any clinically significant adverse change in frequency and/or intensity) of a preexisting condition that is temporally associated with the use of the MSD's product, is also an adverse event.

Changes resulting from normal growth and development that do not vary significantly in frequency or severity from expected levels are not to be considered adverse events. Examples of this may include, but are not limited to, teething, typical crying in infants and children and onset of menses or menopause occurring at a physiologically appropriate time.

Progression of the cancer under study is not considered an adverse event.

All adverse events that occur after the consent form is signed but before beginning the treatment must be reported by the investigator if they cause the subject to be excluded from the trial or are the result of a protocol-specified intervention, including but not limited to washout or discontinuation of usual therapy, diet, placebo treatment or a procedure.

From the time of treatment allocation/randomization through 30 days following cessation of treatment, all adverse events must be reported by the investigator. Such events will be recorded at each examination on the Adverse Event case report forms. The investigator will make every attempt to follow all subjects with non-serious adverse events for outcome. The reporting timeframe for adverse events meeting any serious criteria will be described in next sections.

Adverse events can be spontaneously reported or elicited during open-ended questioning, examination, or evaluation of a subject. (In order to prevent reporting bias, subjects should not be questioned regarding the specific occurrence of one or more AEs.)

The severity and causality will be classified according to the NCI CTCAE v.5 The CTCAE is available for downloading on the internet, see Appendix 11.2.

The adverse event severity grade provides a qualitative assessment of the extent or intensity of an adverse event, as determined by the investigator or as reported by the patients. The severity grade does not reflect the clinical seriousness of the event, only the degree or extent of the affliction or occurrence (e.g. severe nausea, mild seizure), and does not reflect the relationship to study drug.

Severity grade for other adverse events not covered in the toxicity grading scale:

1 = Grade 1	Mild
2 = Grade 2	Moderate
3 = Grade 3	Severe
4 = Grade 4	Life-threatening
5 = Grade 5	Fatal

7.7.1 Main adverse events related to Pembrolizumab
·
7.7.2Definition of an Overdose for This Protocol and Reporting of Overdose to the Sponsor and to MSD. Reporting of pregnancy
Confidential

7.7.2.2Reporting of Pregnancy and Lactation to the Sponsor

Although pregnancy and lactation are not considered adverse events, it is the responsibility of investigators or their designees to report any pregnancy or lactation in a subject (spontaneously reported to them) that occurs during the trial.

Pregnancies and lactations that occur after the consent form is signed but before treatment allocation/randomization must be reported by the investigator if they cause the subject to be excluded from the trial or are the result of a protocol-specified intervention, including but not limited to washout or discontinuation of usual therapy, diet, placebo treatment or a procedure.

Pregnancies and lactations that occur from the time of treatment allocation/randomization through 120 days following cessation of Sponsor's product, or 30 days following cessation of treatment, if the subject initiates new anticancer therapy, whichever is earlier, must be reported by the investigator.

All reported pregnancies must be followed to the completion/termination of the pregnancy. Pregnancy outcomes of spontaneous abortion, missed abortion, benign hydatidiform mole, blighted ovum, fetal death, intrauterine death, miscarriage and stillbirth must be reported as serious events (Important Medical Events). If the pregnancy continues to term, the outcome (health of infant) must also be reported.

7.8Immediate Reporting of Adverse Events to the Sponsor and to Merck

7.8.1 Definition of Serious Adverse Event (SAE)

A Serious Adverse Event is defined as any untoward medical occurrence that at any dose:

- results in death (fatal due to any cause)
- is life-threatening or places the subject, in the view of the investigator, at immediate risk of death from the event as it occurred (Note: This does not include an adverse event that, had it occurred in a more severe form, might have caused death.)Results in or prolongs an existing inpatient hospitalization (hospitalization is defined as an inpatient admission, regardless of length of stay, even if the hospitalization is a precautionary measure for continued observation. (Note: Hospitalization for an elective procedure to treat a pre-existing condition that has not worsened is not a serious adverse event. A pre-existing condition is a clinical condition that is diagnosed prior to the use of IMP and is documented in the patient's medical history.)
- results in persistent or significant disability/incapacity

- is a congenital anomaly/birth defect
- is an important medical event (defined as a medical event(s) that may not be immediately life-threatening or result in death or hospitalization but, based upon appropriate medical and scientific judgment, may jeopardize the subject or may require intervention [eg, medical, surgical] to prevent one of the other serious outcomes listed in the definition above.) Examples of such events include, but are not limited to, intensive treatment in an emergency room or at home for allergic bronchospasm; blood dyscrasias or convulsions that do not result in hospitalization.)
- Suspected transmission of an infectious agent (eg, pathogenic or nonpathogenic) via the study drug is an SAE.
- Although pregnancy, overdose (defined as accidental or intentional dose of a product that is considered both excessive and medically important), and cancer are not always serious by regulatory definition, these events must be handled as SAEs.

Second malignancies are always considered SAEs, no matter when they are diagnosed. These events should be reported on the Serious Adverse Event Forms.(although not serious per ICH definition, is reportable to the Sponsor within 24 hours and to MSD Global Safety (GS) by fax ([name]) within 2 working days to meet certain local requirements)

The following hospitalizations are not considered SAEs:

- a visit to the emergency room or other hospital department < 24 hours, that does not result in admission (unless considered an important medical or lifethreatening event)
- elective surgery, planned prior to signing consent
- admissions as per protocol for a planned medical/surgical procedure
- routine health assessment requiring admission for baseline/trending of health status (eg, routine colonoscopy)
- Medical/surgical admission other than to remedy ill health and planned prior to entry into the study. Appropriate documentation is required in these cases
- Admission encountered for another life circumstance that carries no bearing on health status and requires no medical/surgical intervention (eg, lack of housing, economic inadequacy, caregiver respite, family circumstances, administrative reason).

Progression of cancer under study is not considered an adverse event. All subjects with serious adverse events must be followed up for outcome.

Other definitions

Non-serious adverse event: All adverse events not classifiable as severe.

Unexpected adverse event: An event not described in nature in terms of gravity or incidence and not included in the basic product information (investigator's brochure)

Expected adverse event: An event described in the basic product information (investigator's brochure).

[figure not shown]
Adverse event associated with the use of the drug: Adverse event with a reasonable possibility of being related to the drug (adverse reaction).

The investigator will use the following definitions to evaluate the possible relationship between the adverse event and the medications of the study:

- Not related: Any event, illness or effect of other medications not related with the medication of the study (e.g. if transitory, or not having temporal relationship with the study drug, or presence of a definitive alternative etiology).
- Related: A temporal relationship with the administration of the study drug of the study, which reappears on re-instatement and in which there does not appear to be an alternative etiology

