3.2 Secondary Objective(s) & Hypothesis(es)

- To evaluate the efficacy of Pembrolizumab re-challenge administered 200 mg iv every 21 days in second or further line for advanced NSCLC after progression to check point PD1 / PDL1 inhibitors measured by Progression Free Survival (PFS) per RECIST v1.1 and per modified RECIST. and Overall Survival (OS).
- To evaluate the safety and tolerability profile of Pembrolizumab re-challange administered 200 mg iv every 21 days in second or further line for advanced NSCLC after progression to check point PD1 / PDL1 inhibitors measured by Common Terminology Criteria for Adverse Events (CTCAE) version 4.0 (U.S. Department of Health and Human Services National Cancer Institute National Institutes of Health)

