Antibody directed therapies against check point PD1/PDL1 have demonstrated efficacy in some malignancies, and now are true options in management of metastatic lung cancer. Two monoclonal antibodies directed to PD-1 (Nivolumab, Pembrolizumab) have reach the clinical practice as second line options for NSCLC. Also, monoclonal antibodies directed to PDL1 /PD1 (Atezolizumab, Durvalumab, Avelumab, Pidilizumab) are under investigational exploration. Three anti-PD-1 (Nivolumab, Pidilizumab, Pembrolizumab) and four anti-PD-L1 (BMS-936559, Durvalumab, Atezolizumab, Avelumab) antibodies have been investigated in phase I studies and are under further development in NSCLC (24). In all phase I trials, the maximum-tolerated dose was not reached, and all doses were found to be safe. The frequency of immune-related toxicities from anti-PD-1/anti-PD-L1 treatments appears less than that from anti-CTLA4 treatment. The common drug-related AEs were decreased appetite, anemia, diarrhea, nausea, pruritus, fatigue, pneumonitis, and elevated transaminase (25, 26, 27, 28, 29, 30).

The clinical efficacy of check point PD1/PDL1 inhibitors has been tested and confirmed in four randomized clinical trials. Two phase III trial to compare Nivolumab versus docetaxel in patients that have progression to doublet platinum-based chemotherapy, both squamous or non-squamous NSCLC (20, 21). In the squamous trial Nivolumab resulted in improved overall survival (HR, 0.59, p< 0.001; median 9.2 vs 6 months), PFS (HR: 0.62, p<0.001; median 3.5 vs 2.8 months) and RR (20% vs 9%; p<0.008). The preplanned analysis for

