5.3.2 Dose Modification (Escalation/Titration/Other)

Adverse events (both non-serious and serious) associated with pembrolizumab exposure may represent an immunologic etiology. These adverse events may occur shortly after the first dose or several months after the last dose of treatment. Pembrolizumab must be withheld for drug-related toxicities and severe or life-threatening AEs as per 3 below. See Section 5.8.3.1 for supportive care guidelines, including use of corticosteroids.

[figure not shown]
Table 3

Dose Modification and Toxicity Management Guidelines for Immune-related AEs Associated with Pembrolizumab

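### The 'Not related' causality definition in 7.8.1 lists short duration as a ground in its own right, so a brief drug reaction can be coded unrelated

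*Combined protocol and SAP*

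**What the plan says.** Section 3.2 makes safety a secondary objective: "To evaluate the safety and tolerability profile of Pembrolizumab re-challange administered 200 mg iv every 21 days", measured by CTCAE. Section 7.5.1 makes causality one of the recorded attributes: "Toxicities will be characterized in terms regarding seriousness, causality, toxicity grading, and action taken with regard to trial treatment".

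Under 'Other definitions', section 7.8.1 contains three statements that bear on causality:

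- A drug-associated event is defined as: "Adverse event with a reasonable possibility of being related to the drug (adverse reaction".
- A two-level scale is then introduced as an instruction: "The investigator will use the following definitions to evaluate the possible relationship between the adverse event and the medications of the study".
- 'Not related' is illustrated by "e.g. if transitory, or not having temporal relationship with the study drug, or presence of a definitive alternative etiology". 'Related' needs a temporal relationship with administration, and the event must be one "which reappears on re-instatement and in which there does not appear to be an alternative etiology".

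Relatedness is used elsewhere. Section 5.3.2 states: "Pembrolizumab must be withheld for drug-related toxicities and severe or life-threatening AEs". Section 7.9 attaches SUSAR notification, and the sponsor's communication of possibly related severe events to the marketing authorization holder, to a suspected or possible relationship. Section 7.7 requires every adverse event to be reported through 30 days after treatment ends, whatever its cause. Table 6 collects start and stop dates separately.

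**The concern.** Two of the three example grounds for 'Not related' are evidence about cause: no temporal relationship, and a definite alternative explanation. The third, that the event was transitory, is not. A reaction to a drug can be short, and an unrelated event can be long. Because the grounds are joined by 'or', nothing requires brevity to be combined with either of the others.

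This matters most for events that investigators already expect from this drug class. Section 4.1 reports: "The common drug-related AEs were decreased appetite, anemia, diarrhea, nausea, pruritus, fatigue, pneumonitis, and elevated transaminase". The documents do not say how long such events last. That some cases of nausea, pruritus or diarrhea are brief is an assumption, though an unremarkable one.

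At stake are any summary of treatment-related events and the steps that depend on relatedness in 7.9 and 5.3.2. Every patient here has already received a PD-1 or PD-L1 inhibitor, so attributing reactions on re-challenge is a natural part of reading the safety results.

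**Working it through.** **Text check.** Take an event with a temporal relationship to dosing and no alternative explanation. Under the reasonable-possibility definition it would be expected to count as drug-associated. The two-level scale treats it as follows:

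| Event | As written | Only the transitory ground deleted |
|---|---|---|
| Brief, recurs on re-exposure | Meets 'Related', and also fits an example of 'Not related' | 'Related' |
| Brief, no recurrence or no re-exposure | Fits an example of 'Not related' | Neither category |
| Lasting, recurs on re-exposure | 'Related' | 'Related' |
| Lasting, no recurrence or no re-exposure | Neither category | Neither category |

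Two results follow. First, the transitory ground creates a conflict in row 1 and a route to 'Not related' in row 2. Second, deleting it repairs row 1 only. Rows 2 and 4 are then left without a category, because 'Related' requires recurrence.

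**Direction.** Compared with the same coding without this ground, events can only move into 'Not related'. Any bias the ground introduces into a related-event rate is therefore downward.

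**Size, as illustration only.** The plan states no treatment-related rate, so there is no figure to reproduce. Inputs:

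- N = 110, the maximum enrolment (5.6).
- p = true proportion of patients with at least one drug-related event. Assumed: 60%, varied over 40% and 80%.
- f = share of those patients whose related events were all transitory. Assumed: 10% to 50%.
- Every such event is coded 'Not related'. This is also an assumption, and it is the extreme case.

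Formula: recorded rate = p × (1 − f).

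For p = 0.60 there are 110 × 0.60 = 66 affected patients:

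- f = 0.10: 0.60 × 0.90 = 0.54, or 59.4 patients
- f = 0.30: 0.60 × 0.70 = 0.42, or 46.2 patients
- f = 0.50: 0.60 × 0.50 = 0.30, or 33 patients

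For p = 0.40 the recorded rates at the same f are 0.36, 0.28 and 0.20. For p = 0.80 they are 0.72, 0.56 and 0.40.

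**The case against.** The strongest reply is that the ground is only an example. The operative part of the definition is that the event is not related to study medication, and the word 'transitory' sits in a parenthesis opened by 'e.g.'. Other text points to ordinary clinical assessment: the reasonable-possibility definition directly above, and Table 6, which leaves the relationship to a qualified physician's judgment after weighing listed elements. Those elements are not visible in the public copy and may well set out how time course and other causes are weighed. Section 7.7 also refers causality to CTCAE.

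Much of this stands. A reader might infer that brief reactions are systematically classed as unrelated. The documents support only that they can be. They do not show that brevity decides the coding, and the unseen Table 6 elements cannot be presumed absent or presumed to override 7.8.1. The CTCAE reference adds little, because 7.7 itself says the severity grade does not reflect relationship to drug.

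The reply does not remove the problem. An example in a definition that investigators are told to use is guidance at 19 sites, and one who follows it literally is compliant. Nothing in the readable text cancels it.

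Two further limits are fair. No related-event rate is a named endpoint: 3.2 measures safety by CTCAE, and 8.1 defines only the safety population. And Table 3, which carries the withholding triggers, is not shown, while 5.3.2 covers severe or life-threatening events as a separate limb.

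**Conclusion.** The point holds as a drafting defect with a known direction and an unknown size. Section 7.8.1 allows a short-lived event with a plausible temporal relationship and no other explanation to be coded 'Not related', contrary to the reasonable-possibility definition in the same section. Any bias in related-event summaries is downward. SUSAR notification, communication of possibly related events, and the drug-related wording in 5.3.2 may also be affected. All-causality incidence and grade are not.

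Three stronger conclusions might be drawn and are not supported:

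- That the safety results as a whole are biased low. Events are collected regardless of cause.
- That a particular number of patients will be misclassified. The fall from 60% to between 54% and 30% rests wholly on assumed values of p and f and on full adherence to an example.
- That a brief reaction will escape the withholding instruction. The triggers cannot be read in this copy.

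Nor is the transitory ground the only source of under-attribution: the recurrence requirement in 'Related' works in the same direction.

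**What to change.** Make one edit to 7.8.1 with three parts:

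1. Delete 'if transitory, or' from 'Not related', leaving absence of a temporal relationship and a definitive alternative etiology as the example grounds.
2. Keep duration only in the start and stop dates already collected in Table 6.
3. Reconcile the 'Related' definition with the reasonable-possibility wording, so that recurrence on re-exposure supports a relationship but is not required and every event fits exactly one category. Check the causality elements in Table 6 against the result.

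Part 1 alone is not enough, because a single brief reaction that is not re-tested would then fit neither category.

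The cost is a small text change and a note to sites. The related-event rate may look slightly less favourable afterwards.

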5.10 Subject Withdrawal/Discontinuation Criteria

Subjects may withdraw consent at any time for any reason or be dropped from the trial at the discretion of the investigator should any untoward effect occur. In addition, a subject may be withdrawn by the investigator or the Sponsor if enrollment into the trial is inappropriate, the trial plan is violated, or for administrative and/or other safety reasons.

Specific details regarding discontinuation or withdrawal are provided in section 7.6.1.

A subject must be discontinued from the trial for any of the following reasons:

- The subject or legal representative (such as a parent or legal guardian) withdraws consent.
- Confirmed radiographic disease progression

Note: A subject may be granted an exception to continue on treatment with confirmed radiographic progression if clinically stable or clinically improved. All these cases must be approved by Trial Chair before starting the treatment beyond progression.

- Unacceptable adverse experiences
- Intercurrent illness that prevents further administration of treatment
- Investigator's decision to withdraw the subject
- The subject has a confirmed positive serum pregnancy test
- Noncompliance with trial treatment or procedure requirements

- The subject is lost to follow-up
- Completed 24 months of uninterrupted treatment with pembrolizumab or 35 administrations of study medication, whichever is later.

Note: 24 months of study medication is calculated from the date of first dose.

Administrative reasons

[figure not shown]
Confidential

The End of Treatment and Follow-up visit procedures are listed in Section 6 (Protocol Flow Chart). After the end of treatment, each subject will be followed for 30 days for adverse event monitoring (serious adverse events will be collected for 90 days after the end of treatment as described in section 7.9.). Subjects who discontinue for reasons other than progressive disease will have post-treatment follow-up for disease status until disease progression, initiating a non-study cancer treatment, withdrawing consent or becoming lost to follow-up. After documented disease progression each subject will be followed by telephone for overall survival until death, withdrawal of consent, or the end of the study, whichever occurs first.

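### Section 7.8.1 sets two incompatible causality standards; read literally, a fatal event or one that permanently ends treatment at first occurrence cannot be classed as Related

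*Combined protocol and SAP*

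**What the plan says.** All places are in the combined protocol and SAP.

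- **7.8.1, other definitions.** An event associated with use of the drug is defined as: "Adverse event with a reasonable possibility of being related to the drug (adverse reaction").
- **7.8.1, relationship scale.** The text that follows is an instruction: "The investigator will use the following definitions to evaluate the possible relationship between the adverse event and the medications of the study". Only two categories are listed. *Related* is a temporal relationship with study drug administration, "which reappears on re-instatement and in which there does not appear to be an alternative etiology". *Not related* is illustrated by "e.g. if transitory, or not having temporal relationship with the study drug, or presence of a definitive alternative etiology".
- **7.7.** Causality, together with severity, is to be classified by CTCAE.
- **7.9.** The sponsor's report to the marketing authorisation holder is triggered by a third term, *possibly related*. SUSARs must also be notified.
- **Table 6, closing sentence.** A qualified physician reports the relationship on the case report form, using clinical judgment and the elements listed above that sentence. Those elements are not visible in the public text.

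A secondary wording problem lies alongside. The other definitions in 7.8.1 state: "Non-serious adverse event: All adverse events not classifiable as severe". Section 7.9 also uses *severe* for the events to be notified immediately. The SAE criteria in 7.8.1 rest instead on outcomes, for example "results in death (fatal due to any cause"), or an inpatient admission "regardless of length of stay, even if the hospitalization is a precautionary measure for continued observation".

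**The concern.** Reasonable possibility is a threshold of suspicion. Reappearance on re-instatement is evidence that can exist only if the patient survives, the event resolves and the drug is given again. A scale that demands it excludes events for which that sequence cannot happen, and these include the most serious ones.

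The protocol expects such events. Death is the first SAE criterion, "Unacceptable adverse experiences" is a ground for discontinuation in section 5.10, and section 5.3.2 says that events may arise months after the last dose.

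Safety and tolerability of re-challenge is a secondary objective (section 3.2), and section 7.5.1 requires causality and seriousness to be characterised for toxicities. If some sites apply the literal scale and others apply reasonable possibility, recorded causality depends on the site as well as on the event. Any table of treatment-related events, and the identification of suspected reactions, inherits that inconsistency.

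**Working it through.** There is no figure in the plan to reproduce, and no arithmetic applies. The check is a comparison of texts.

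**Step 1: is reappearance optional?** The *Related* entry has three parts: temporal relationship, reappearance on re-instatement, no apparent alternative cause. They are joined as cumulative conditions. Nothing limits reappearance to patients who are re-treated, offers it as an alternative or marks it as an example. The neighbouring *Not related* entry does mark its criteria as examples, so the difference is visible on the page.

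**Step 2: apply each standard to the same events.** Suppose in each case that timing is plausible and no other cause is apparent.

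| Event | Reasonable possibility | *Related* as written |
|---|---|---|
| Fatal | Can be met | Cannot be met: no re-instatement |
| Permanently ends treatment at first occurrence | Can be met | Cannot be met: no re-instatement |
| Starts after the last dose | Can be met | Ordinarily not met; possible only if treatment restarts |
| Occurs on treatment, dosing resumes, does not recur | Can be met | Not met |
| Occurs on treatment, dosing resumes, recurs | Can be met | Met |

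The third row is qualified because section 7.6.1 gives patients who reach CR or complete 24 months of treatment an option to restart, under criteria not visible here.

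**Step 3: where do the excluded events go?** In the first four rows, an event that was not transitory matches none of the *Not related* examples either: timing fits and no other cause is established. The scale gives it no category. If it was transitory, it matches a *Not related* example on that ground alone, although a reaction that resolves can still be due to the drug.

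**Step 4: does other visible text settle it?**
- Section 7.7 points to CTCAE for causality, but the grades it lists are severity grades, and the section itself says that the grade does not reflect relationship to study drug.
- Section 7.9 uses *possibly related*, which 7.8.1 does not define.
- Table 6 ends in clinical judgment. That is compatible with reasonable possibility, but it does not cancel the instruction in 7.8.1.

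The visible text thus gives several causality wordings and no order of precedence.

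**Step 5: the secondary wording.** Section 7.7 says that the severity grade does not reflect clinical seriousness. A grade 1 or 2 event with a precautionary admission is an SAE under the 7.8.1 criteria, yet non-serious under the other definitions read literally. A grade 3 event that meets no SAE criterion would be notified immediately under 7.9 read literally.

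**The case against.** The best defence is that practice will probably not follow the literal scale. The visible close of Table 6 says how the relationship reaches the case report form, and it names a physician's judgment over several elements, not compulsory re-exposure. That makes an all-or-nothing application less likely. It does not remove the definition that 7.8.1 tells the investigator to use, so the conflict stands.

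The defence also limits the consequences, and here it largely succeeds.

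- **Notification.** A reader might infer that drug-related deaths would go unreported. The documents do not support this. Section 7.9 requires immediate notification of *severe* events, by which it probably means serious ones, without any causality condition, and death from any cause is an SAE. The trigger for the marketing authorisation holder is *possibly related*, which is close to reasonable possibility. What remains exposed is the recorded causality and the classification of an event as a suspected reaction.
- **Late events.** A reader might infer that no post-treatment event can ever be *Related*. The restart option in 7.6.1 makes that too absolute. Moreover, adverse events are collected for 30 days after treatment (7.7) and serious ones for up to 90 days (2.3 and 5.10), so many very late events fall outside collection whatever the wording.
- **Analysis.** Section 3.2 measures safety by CTCAE, and section 8.1 defines a safety population but names no analysis or decision rule that uses a related-event rate.
- **Severe and serious.** This is probably a drafting slip, and both 7.8.1 and Table 6 define seriousness by outcome. It merits correction but is secondary.

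**Conclusion.** The inconsistency is real and can be seen within section 7.8.1 alone. The scale the investigator is told to use cannot class as *Related* a fatal event or one that permanently ends treatment at first occurrence, and ordinarily cannot do so for an event starting after the last dose. The protocol's own definition of a drug-associated event can admit all three.

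The likely effect is inconsistency between sites, with any bias in treatment-related counts and SUSAR identification running downward. Its size cannot be derived: there are no event rates in the documents, and the relationship elements of Table 6 are not visible and may contain a workable scale. A reader might infer that related events will be undercounted; the documents show only that the literal rule would allow it. The conclusion rests on reading the *Related* entry as written.

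ORR, PFS, OS, the sample size and decision rule, and adverse event incidence by grade regardless of cause are not affected.

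**What to change.** - **7.8.1, causality.** Define *Related* by the protocol's own reasonable-possibility standard, with recurrence on re-administration as supporting evidence only. Define *Not related* as no reasonable possibility, and delete the example of a transitory event.
- **7.7.** Limit CTCAE to severity.
- **7.9 and Table 6.** Reconcile *possibly related* and the Table 6 relationship elements, including those not visible here, with the single definition in 7.8.1. Check that the case report form guidance matches.
- **Secondary correction.** In 7.8.1, define a non-serious event as one meeting none of the SAE criteria; in 7.9, replace *severe* with *serious*.

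The cost is wording only. Visits, sample size and efficacy analyses do not change. Reported related rates may rise, because events that the literal scale shuts out could then be classed as *Related*.
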